Circulating blood cells are an easily obtainable source to examine bioenergetics and would be a preferred non-invasive alternative to collecting tissue biopsies, especially in children. Bioenergetic profiling of circulating cells has been used as a measure of systemic mitochondrial fitness, physical function and inflammation²⁷⁻²⁹. While circulating blood cell bioenergetics has not been compared between lean and obese individuals, peripheral blood monocyte bioenergetics was compared in morbidly obese adults before and after bariatric surgery, with observed post-surgery increase in basal and maximal mitochondrial respiration that was also correlated with increased skeletal muscle maximal respiration³⁰. Another recent report indicated that the monocyte and platelet maximal respiratory capacity correlated with the bioenergetics in both skeletal and cardiac muscle³¹. These studies suggests that bioenergetic profiling of circulating cells largely reflects the bioenergetic capacity of other tissues.

The main purpose of the proposed investigation is to fill a critical research gap and gain insight into the pathophysiology of obesity and insulin resistance in childhood by establishing, for the first time, whether obese insulin resistant children exhibit reduced antioxidant/redox capacity and abnormal bioenergetics in circulating blood cells as compared to normal weight and obese insulin sensitive children, and whether REE and FAO are correlated with abnormal redox status

and bioenergetics. In addition, not all obese subjects are metabolically unhealthy (MUO) and body mass index (BMI) may not be the best determinant of metabolic health. Fat mass, on the other hand is correlated with insulin resistance, particularly visceral adiposity. Metabolically healthy obese (MHO) have no signs of the metabolic syndrome, (cardiometabolic risk, hypertension and dyslipidemia), including children. Therefore, a repeated measures study at 12 months post baseline on obese children will help establish not only the degree of change in the studied outcomes, but also their predictive value for T2D development ^{32, 33}. The findings from these studies will lay the foundation needed for future investigations into identifying the cellular and molecular

[figure not shown]

Figure 1: A: Metabolically unhealthy (MU), lipodystrophy; B: MU, obese; C: Metabolically healthy (MH) obese

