mechanisms of insulin resistance, and the development of a non-invasive biomarker in children at an increased risk of developing insulin resistance.

Hypothesis and Specific Aims

We hypothesize that when compared to normal weight or obese insulin sensitive children, obese insulin resistant children will exhibit altered circulating blood cell bioenergetics and a more oxidized plasma redox state and that these alterations will be associated with decreased resting energy expenditure and impaired fatty acid oxidation (FAO). Furthermore, we hypothesize that poor oxidative capacity over time may distinguish between metabolically healthy obese (MHO) and metabolically unhealthy obese (MUO) phenotypes, as well as be predictive of T2D development. We also hypothesize that bioenergetics, REE and FAO will be improved in obese T2D or insulin resistant children after 6 months of metformin therapy that will be prescribed as part of their clinical care. To test these hypotheses, we will evaluate the following Specific Aims:

Specific Aim 1: Determine whether peripheral blood mononuclear cell (PBMC) and platelet bioenergetics (oxidative phosphorylation, glycolysis and fatty acid oxidation) are impaired and whether plasma glutathione-mediated redox/antioxidant capacity is decreased in obese insulin resistant children as compared to normal weight and obese insulin sensitive children.

Specific Aim 2: Determine whether resting energy expenditure (REE) and fatty acid oxidation (FAO) are decreased in obese insulin resistant as compared to lean and obese insulin sensitive children and whether REE and FAO are correlated with bioenergetic and redox profiles.

Specific Aim 3: Determine whether the bioenergetic oxidative capacity measured in circulating cells, PBMCs/platelets, and FAO are valuable predictive markers of T2D in obese children, in addition to distinguishing MUO from MHO subjects.

Specific Aim 4: Determine whether circulating blood cell bioenergetics and whole-body REE and FAO are modulated by metformin therapy that will be prescribed as part of clinical care in

Title: Bioenergetics and Metabolism in Pediatric Populations

PI: [name].

obese children with T2D or insulin resistance.

Study Design and Procedures

This study consists of:

1. An observational cross sectional bioenergetic and metabolic analysis of several groups of children including lean, obese, and T2D.

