2. A longitudinal bioenergetic and metabolic analysis of obese children that will be followed for 12 months, repeated measures will be taken at 12 months post-baseline.
3. A prospective bioenergetic and metabolic analysis of obese insulin resistant children (Aim 3) and newly diagnosed children with T2D or insulin resistance who will be prescribed metformin as part of their clinical care (Aim 4).

A prospective subject and his/her parent will come for the study visit that will last up to 4 hours. A subject (and/or his/her parent) will be asked questions regarding the subject's medical history that will be reviewed by study staff to identify patients who fulfill inclusion/exclusion criteria. In addition, study staff may review medical records from ACH or other healthcare practitioners (such as physicians or pharmacists) outside ACH in order to confirm the inclusion/exclusion criteria. Information from medical records may be collected from the time of consent up until the time that data analysis for this study is complete and results have been published. Study staff will ask parents about demographic information including biologic gender, date of birth, race/ethnicity, and parental occupations as well as grade in school.

Prior to the study visit, study staff may contact the parent and ask for medications that the participant is currently taking and may ask of any new health diagnoses. In the event that the participant is taking medications or has a new health diagnosis that may cause him/her to be ineligible to participate in the study visit, the study visit may be rescheduled or canceled. Study staff may contact a parent and send the IRB approved consent form and information regarding the scheduled visit to the parent(s) prior to the scheduled date. If the consent form has been revised since the last informed consent discussion, the new IRB approved consent form may be sent to parents. If applicable, the parent will be informed of the blood draw and advised that if the parent wishes their child to complete the blood draw at the visit, the child will need to be fasting including no food or liquid after 12 am, except for water and medications the day of the visit.

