For Aim 3: A paired t-test will be used to compare the mean change in the various outcomes described in SA1 and SA2 from baseline to 12 months for pre-pubertal insulin resistant obese children. If the assumptions for the paired t-test are not met, the non-parametric Wilcoxon matched-pairs signed-ranks test will be used. Alternatively, generalized linear mixed models (GLMM) will be used for Aim 3. GLMM account for the dependence between measurements from the same individual taken over time and allow the inclusion of fixed and time varying covariates.

For Aim 4: A paired t-test will be used to compare the effects of metformin on the various outcomes on obese T2D/insulin resistant children with a new metformin prescription. If the assumptions for the paired t-test are not met, the non-parametric Wilcoxon matched-pairs signed-ranks test will be used. Alternatively, generalized linear mixed models (GLMM) will be used for Aim 4. GLMM account for the dependence between measurements from the same individual taken over time and allow the inclusion of fixed and time varying covariates.

Sample Size Justification:

For Aims 1 and 2, statistical power was computed based on a one-factor ANOVA with a total of 110 children (70 obese insulin resistant, 20 healthy obese, 20 healthy lean). Assuming 80% power and $\alpha = 0.05$, the minimum detectable Cohen's f effect size (ES(f)) is 0.33. This is a medium effect size and should provide valuable information regarding whether a large study is warranted.

For Aim 3, statistical power was computed based on a paired t-test with a total of 40 children. Assuming 80% power and $\alpha = 0.05$, the minimum detectable Cohen's d effect size (ES(d)) is 0.45 for those who completed the study. These are medium effect sizes and should provide valuable information regarding whether a large study is warranted.

For Aim 4, statistical power was computed based on a paired t-test with a total of 10 children. Assuming 80% power and $\alpha = 0.05$, the minimum detectable Cohen's d effect size (ES(d)) is 1.0. Although this effect size is large, it should provide valuable information regarding whether a large study is warranted.

Ethical Considerations

This study will be conducted in accordance with all applicable government regulations and University of Arkansas for Medical Sciences research policies and procedures. This

Title: Bioenergetics and Metabolism in Pediatric Populations

PI: [name].

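### Aim 3 asks whether the markers predict type 2 diabetes, but its analysis estimates only mean 12-month change; for MUO versus MHO the plan offers a baseline comparison of means, not a measure of discrimination

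*Combined protocol and SAP*

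**What the plan says.** **The question.** In Hypothesis and Specific Aims, Aim 3 asks whether circulating-cell oxidative capacity and FAO "are valuable predictive markers of T2D in obese children, in addition to distinguishing MUO from MHO subjects". The hypothesis adds a time element: "we hypothesize that poor oxidative capacity over time may distinguish between metabolically healthy obese (MHO) and metabolically unhealthy obese (MUO) phenotypes". Study Design and Procedures repeats both purposes for the 12-month visit and puts degree of change beside them.

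**The analysis.** For Aim 3, Data Analysis specifies: "A paired t-test will be used to compare the mean change in the various outcomes described in SA1 and SA2", from baseline to 12 months, in pre-pubertal insulin-resistant obese children. A signed-ranks test is the fallback. It continues: "Alternatively, generalized linear mixed models (GLMM) will be used for Aim 3". The mixed model is described as handling within-child dependence and as able to "allow the inclusion of fixed and time varying covariates". No response, phenotype term or covariate is named. The Sample Size Justification powers Aim 3 on the paired t-test with 40 children, giving a detectable d of 0.45.

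**The phenotypes.** The background says: "Metabolically healthy obese (MHO) have no signs of the metabolic syndrome". The Tanner stage item under Study Procedures uses a different working meaning: it warns that insulin resistance caused by puberty could be mistaken for MUO, which makes insulin resistance the mark of MUO.

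**Who is followed.** The background says "a repeated measures study at 12 months post baseline on obese children will help establish" the degree of change and predictive value, and design item 2 reads "A longitudinal bioenergetic and metabolic analysis of obese children that will be followed for 12 months". Design item 3, the visit schedule, the compensation paragraph and the Aim 3 analysis all point to the insulin-resistant group. Healthy obese children are compensated for a single visit.

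**The concern.** A paired test of mean change contains no T2D outcome and no link between a child's baseline marker and that child's later state. Whether it is significant or null, it says nothing about prediction. A marker can shift on average without predicting anything, and can predict well with no mean shift.

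If the plan is followed exactly, the prediction half of Aim 3 ends without an estimate. The outcome, marker and model for any prediction statement would then be chosen after the data are seen, from a broad set of outcomes carried over from Aims 1 and 2. The MUO/MHO half is in a better position, because one planned baseline contrast bears on it, but that contrast does not measure how well a marker separates the two phenotypes.

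**Working it through.** **1. The plan's own figure.** Inputs from the Sample Size Justification: n = 40, 80% power, alpha 0.05 (sidedness not stated; two-sided assumed). For a paired t-test, T is noncentral t with 39 df and noncentrality d√40. Solving for 80% power gives d = 0.454; at d = 0.45, power is 79.3%. A one-sided test would give 0.400, so the stated 0.45 is the two-sided figure and is right. The sample size also agrees with the visit plan: 70 × (1 − 0.43) = 39.9. This figure powers mean change only.

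**2. Question against analysis.**

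| Part of Aim 3 | What would answer it | What is specified |
|---|---|---|
| Degree of 12-month change | Paired comparison | Paired t-test, signed-ranks test or mixed model |
| Prediction of T2D | Later outcome modelled on baseline marker | Nothing |
| MUO vs MHO at baseline | Phenotype definition and a discrimination measure | ANOVA/GLM contrast of means, healthy obese (20) vs insulin resistant (70), powered for Aims 1 and 2 |
| MUO vs MHO over time | Both phenotypes followed, with a phenotype-by-time term | No such term; if insulin resistance marks MUO, no MHO children are followed |

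**3. T2D cases to expect.** No rate is given. Take an assumed 12-month risk p, with expected cases 40p and chance of none (1 − p)^40:
- p = 0.5%: 0.2 cases, chance of none 82%
- p = 1%: 0.4 cases, 67%
- p = 2%: 0.8 cases, 45%
- p = 5%: 2 cases, 13%

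Medical records may be collected until publication, so later cases could be added, but finding T2D cases is not a stated purpose of that collection.

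**4. What 40 children could support.** Regress the 12-month insulin/glucose index on a baseline marker with k = 4 adjustment covariates. The detectable partial correlation (80% power, two-sided 0.05) is tanh[(1.960 + 0.842)/√(n − 3 − k)]. At n = 40 this is tanh(2.802/√33) = tanh(0.488) = 0.452, about 20% of residual variance. Bonferroni for 2, 3 or 5 markers raises it to 0.49, 0.51 or 0.53. If an assumed 10%, 20% or 30% of children are set aside for puberty or metformin (n = 36, 32, 28), it is 0.48, 0.51 or 0.55.

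**5. Baseline AUC, 70 vs 20, assumed AUC A = 0.70.** The Hanley-McNeil variance is [A(1 − A) + (m − 1)(a − A²) + (n − 1)(b − A²)]/(mn), where m is the number of positives, n the number of negatives, a = A/(2 − A) = 0.5385, b = 2A²/(1 + A) = 0.5765 and A² = 0.49.
- The 70 as positives: (0.21 + 69 × 0.0485 + 19 × 0.0865)/1400 = 5.197/1400, SE 0.061, 95% CI 0.58 to 0.82.
- The 20 as positives: (0.21 + 19 × 0.0485 + 69 × 0.0865)/1400 = 7.097/1400, SE 0.071, 95% CI 0.56 to 0.84.

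**6. Phenotype by time.** If a metabolic-syndrome definition split the 40 returning children 20/20, 30/10 or 35/5 (assumed), a two-sample noncentral t-test detects a difference in change of 0.91, 1.05 or 1.37 SDs of change. That is exploratory territory.

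**The case against.** Four defences deserve an answer.

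- **The mixed model could do it.** It could carry a phenotype-by-time term, since covariates are allowed. But the plan does not say so, and Aim 4 has the same wording, so this is not a prediction model written for Aim 3.
- **The baseline ANOVA compares the phenotypes.** This largely stands. A reader might infer that the plan has no MUO/MHO comparison at all, and the documents do not support that. On the working meaning in the Tanner item, the healthy-obese versus insulin-resistant contrast is a baseline comparison of MHO and MUO means, with a GLM for covariates. Its limits are that it is not a discrimination measure, it is powered for Aims 1 and 2, and the background describes MHO differently.
- **The study is exploratory.** The sample size text presents the results as a guide to whether a large study is warranted. That excuses modest power, but not estimating a different quantity. Degree of change is a stated purpose and is properly served.
- **The proposed regression has weaknesses of its own.** This stands. All the children followed are insulin resistant at entry, so the index has a restricted range and correlations may be weakened. The blood assays are worded permissively. The choice of index and covariates is a design preference; what is necessary is to specify a prediction analysis or narrow the aim.

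A reader might also infer a substantive conflict over which obese children are followed. The background and design item 2 are looser, but design item 3, the visit schedule, the compensation text and the analysis section agree on the insulin-resistant group. This is loose wording.

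**Conclusion.** The concern holds for prediction of T2D: no specified analysis can support such a statement, and the number of cases likely in 40 children over 12 months (0.2 to 2 at the assumed rates) would not rescue one.

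It holds in part for MUO versus MHO. A baseline comparison of means exists if insulin resistance defines MUO; a discrimination measure does not. On that same definition the 12-month cohort has no MHO children, so the hypothesis about separating the phenotypes over time cannot be tested. Under a metabolic-syndrome definition it might be, with unknown group sizes.

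Nothing here faults the stated d of 0.45 or the paired test as an analysis of change, and Aims 1, 2 and 4 are not affected. The T2D rates, the AUC of 0.70, the phenotype splits and the proportions set aside are assumptions. They show what the added analyses could deliver; the mismatch between aim and analysis does not depend on them.

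**What to change.** 1. Keep the paired analysis for degree of change. Add, as the Aim 3 prediction analysis, a regression of the 12-month fasting insulin/glucose index on one prespecified baseline bioenergetic or FAO marker, adjusted for the baseline index and a short prespecified covariate list (for example age, sex and BMI z-score, making four in all). State the detectable partial correlation, note that range restriction may weaken the association, and give a multiplicity rule if more markers are tested. Report how many children entered puberty or started metformin by 12 months, with a sensitivity analysis setting them aside.
2. State whether MUO and MHO mean the recruitment groups or the presence or absence of metabolic-syndrome signs. Report a baseline AUC with 95% CI for the same marker; if the contrast is 70 vs 20, quote the SE as 0.061 to 0.071 at an assumed AUC of 0.70. Drop the over-time phenotype claim unless both phenotypes occur among returning children. If they do, add a phenotype-by-time term to the mixed model, name its response and covariates, and label it exploratory.
3. Restate the Aim 3 conclusion as progression of insulin resistance and baseline discrimination, not prediction of T2D.
4. Editorially, align the background and design item 2 with design item 3, the visit schedule and the compensation paragraph on who is followed.

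**Cost.** Wording, definitions and a little more analysis. Waist, blood pressure, Tanner stage, insulin, glucose and lipids are already among the planned procedures, and additional visits repeat them, so no visits, samples or participants are added. The price is a narrower claim.

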- Participants in the obese-insulin resistant group may be asked to complete one additional study visits to occur at 12 months (\pm 2 weeks) after the initial study visit. This is to follow changes in bioenergetic and metabolic parameters over time to assess validity and will help establish not only the degree of change in the studied outcomes, but also their predictive value for T2D development, in addition to distinguish between metabolically healthy obese (MHO) and metabolically unhealthy obese (MUO) phenotypes. We may request that all obese insulin resistant participants complete one additional study visit; however, this additional study visit is optional as we do not want to discourage potential enrollment due to the possibility of another visit or lengthy visit. We anticipate roughly 43% of the 70 obese insulin resistant participants will decline a 2nd study visit with a goal of 40 subjects completing a second visit at 12 months (\pm 2 weeks).
- Participants in the newly prescribed metformin group who are prescribed metformin as part of their clinical care will be asked to complete a second study visit to occur six months (\pm 2 weeks) after beginning metformin therapy prescribed as part of their clinical care. We may request that all 20 participants in this group complete the additional study visit; however, the additional study visit is optional as we do not want to discourage potential enrollment due to the possibility of multiple visits or lengthy visits. We anticipate 50% of the 20 participants in this group will decline a 2nd study visit with a goal of 10 subjects completing a 2nd visit at 6 months (\pm 2 weeks).

A participant/parent pair will be compensated \$100.00 in gift cards for each study visit completed. Completion of the study visit may include participation in parental study forms, anthropometric

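### Aims 3 and 4 lead with a paired t-test on children who choose to return; the mixed model that could use every baseline is an alternative with no rule for its use

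*Combined protocol and SAP*

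**What the plan says.** In Data Analysis, the Aim 3 paragraph begins: "A paired t-test will be used to compare the mean change in the various outcomes described in SA1 and SA2". The change runs over the year after baseline, and the population named is pre-pubertal obese children with insulin resistance. If its assumptions fail, "the non-parametric Wilcoxon matched-pairs signed-ranks test will be used", and that test also needs complete pairs. The paragraph then adds: "Alternatively, generalized linear mixed models (GLMM) will be used for Aim 3". The reasons given for the mixed model are within-child dependence and the use of covariates; missing follow-up is not mentioned. The Aim 4 paragraph has the same structure.

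The text on additional visits in Study Design and Procedures explains that "this additional study visit is optional as we do not want to discourage potential enrollment". On numbers it says: "We anticipate roughly 43% of the 70 obese insulin resistant participants will decline a 2nd study visit". The target is therefore 40 children seen twice. For the metformin group it expects half of 20 to decline, leaving 10.

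Sample Size Justification follows the completers: "For Aim 3, statistical power was computed based on a paired t-test with a total of 40 children", and Aim 4 is powered on 10. The documents give no missing-data assumption, no comparison of returners with decliners, and no sensitivity analysis for non-return.

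**The concern.** Non-return is expected, large and voluntary. A paired test describes only those who come back. Suppose children with higher (or lower) baseline values return more often. Regression to the mean then makes their average change differ from zero even if nothing changed in the group as a whole. The Aim 3 paragraph names insulin resistant obese children as its population, without limiting it to those willing to return, so selection could be reported as a 12-month change.

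The mixed model could address this by using the baselines of decliners. As written, however, nothing says when it replaces the t-test, which effects it contains, or whether baseline-only children enter. The choice could therefore be made after the data are seen.

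**Working it through.** **Reproducing the plan's figures.** For a two-sided paired t-test at alpha 0.05 the noncentrality is d × √n.
- Aim 3: 0.45 × √40 = 2.85 on 39 df gives 79.3% power; the exact minimum detectable d is 0.454.
- Aim 4: d = 1.0 with n = 10 gives 80.3% power; the exact value is 0.996.
- Non-return: 43% of 70 is 30.1, leaving 40; 50% of 20 is 10.

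The stated figures hold.

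**Inputs not in the documents (assumed).** Visit-to-visit correlation ρ is 0.4 to 0.6 with equal SDs at both visits. The correlation c between a latent tendency to return and the baseline value is 0 to 0.5. There is no true change.

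**Bias of the paired change.** Bias = (ρ − 1) × m, where m is the returners' mean baseline in SD units relative to all 70. If the top 40 of 70 on the latent score return, p = 40/70 = 0.571, the normal cut-off is −0.180 and its density is 0.393. So m = c × 0.393/0.571 = 0.687c. For example, c = 0.3 and ρ = 0.4 give m = 0.206 and bias −0.6 × 0.206 = −0.124. The sign reverses if children with lower baselines return.

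Type I error below is from simulation (40,000 runs per setting, bivariate normal, no covariates):

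| c | Size of bias in SD, ρ = 0.4 | Type I error | Size of bias in SD, ρ = 0.6 | Type I error |
|---|---|---|---|---|
| 0 | 0 | 5% | 0 | 5% |
| 0.1 | 0.04 | 5% | 0.03 | 5% |
| 0.2 | 0.08 | 7% | 0.05 | 7% |
| 0.3 | 0.12 | 11% | 0.08 | 9% |
| 0.5 | 0.21 | 22% | 0.14 | 16% |

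Separate runs put the most extreme setting as high as 23%.

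**Cross-check with a different return model.** With logistic return averaging 40/70 and an odds ratio of 0.5 or 2 per baseline SD, m is 0.27 in size. Bias is 0.19, 0.13 and 0.08 SD at ρ = 0.3, 0.5 and 0.7, with type I error of about 17%, 13% and 10%. At an odds ratio of 1.5, bias is 0.05 to 0.12 SD and type I error about 7 to 9%.

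**Using all 70 baselines.** The likelihood estimate of the follow-up mean is the returners' follow-up mean plus b × (baseline mean of all 70 − baseline mean of returners), where b is the returners' regression slope of follow-up on baseline. Subtracting the baseline mean of all 70 gives the change. In the settings tabulated, bias stayed within 0.003 SD and type I error was about 5% with an unbiased variance and a t reference.

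**Precision under random return.** The variance is (1 − ρ²)/40 + (1 − ρ)²/70, against 2(1 − ρ)/40 for 40 pairs.
- ρ = 0.4: 0.0261 against 0.0300, SE ratio 0.934.
- ρ = 0.6: 0.0183 against 0.0200, SE ratio 0.956.

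The simulated ratios, with the slope estimated, were 0.94 and 0.96: an SE about 4 to 6% smaller. At c = 0.5 this gain disappears (ratios 1.00 and 1.03), so bias is the main reason for the change.

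**Aim 4 (20 baselines, 10 returners, same assumptions).** Paired type I error is 5% under random return and rises to about 10% at c = 0.5, ρ = 0.4. An uncorrected Wald test of the likelihood estimate rejects in about 10% of runs, even under random return. With an unbiased variance and a t reference it rejects in about 4%. Kenward-Roger itself was not simulated.

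**The case against.** The plan already names the mixed model for both aims and labels no analysis as primary. That the t-test leads is inferred from sentence order, the word introducing the mixed model, and the power calculation. This is fair, but it locates the gap rather than closing it: two analyses with no priority and no missing-data assumption are not a specification.

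A reader might infer four stronger things that the documents do not support:
- **That 30 children are discarded from the study.** Their baselines serve Aims 1 and 2, which are powered on 110 children including all 70. They are unused only in the paired change analysis.
- **That the paired result will be biased, with error of 9 to 23%.** No figure in the documents links return to baseline. The optional visit is explained by visit burden, not by disease status. Mild selection gives 5 to 7%, and random return gives no bias.
- **That the paired t-test is invalid.** For the children who return, it is a legitimate test of their mean change. The bias is relative to the full group.
- **That the stated detectable effects are wrong.** They reproduce, and the Aim 3 figure is stated for completers.

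Two further objections stand. The study is framed as informing whether a larger one is warranted, which limits the stakes of an inflated type I error. And simply moving Aim 4 to a mixed model with an uncorrected Wald test would be no improvement.

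**Conclusion.** The concern holds in conditional form. The lead analysis for Aims 3 and 4 depends on voluntary return, and the analysis that protects against return driven by the observed baseline is named but unspecified. The bias needs two conditions: return related to baseline, and a regression slope of follow-up on baseline different from 1, which is usual when visits correlate imperfectly.

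For Aim 3 the plausible size runs from nothing to about 0.2 SD, depending entirely on the assumed correlations. The mechanism is certain; its size in this study is not known. The change is worth making because it is cheap and uses data already collected.

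**What to change.** In the Aim 3 and Aim 4 paragraphs of Data Analysis:
- Make a likelihood-based (REML) mixed model the primary change analysis, with visit as a fixed effect. State that all 70 baselines (20 for Aim 4) enter, and name any covariates in advance.
- Specify a small-sample correction such as Kenward-Roger degrees of freedom. For Aim 4 this is essential.
- State the missing-at-random assumption.
- Keep the paired t-test, with its Wilcoxon fallback, as a completer sensitivity analysis.
- Tabulate baseline values of returners and decliners.

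The cost is wording only: no new data or visits. The downsides should be stated. The model does not correct for return that depends on the unseen follow-up value, and the corrected test is slightly conservative with 10 returners (about 4% in the check above).
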